*Mild psoriasis - psoriasis affected Body Surface Area (BSA) less than 10% and Psoriasis Area and Severity Index (PASI) between 6 and 12.
*Group 1 : 6 months secukinumab + 12 months observation
*Group 2 : 3 months placebo + 3 months secukinumab + 12 months observation
- 2) To explore whether secukinumab will prevent relapses after medication has been discontinued in subjects with mild plaque-type psoriasis.
- 3) To compare frequency of relapse between subjects who achieve a score of 0 (clear) on IGA (Investigator's Global Assessment) and subjects who do not achieve a score of 0 (clear) on IGA, within each group (Group 1 (6 months secukinumab) and Group 2 (3 months Placebo + 3 months secukinumab)).
- 4) To compare frequency of relapse between subjects who achieve a score of 0 (clear) on IGA between group 1 and group 2 (Group 1 (6 months secukinumab) and Group 2 (3 months Placebo + 3 months secukinumab)).
- 5) To evaluate the safety of secukinumab for the treatment of subjects with mild plaque-type psoriasis comparing the secukinumab-receiving mild psoriasis subjects (Group 1) and the placebo-receiving mild psoriasis subjects (Group 2) for 3 months.

12.7 * Primary Outcome(s)

Indicate which *variable(s)* will be assessed to judge the primary specific aim. Give measurement units, if applicable.

- 1) The proportion of subjects who have a reduction of 75% or more from baseline in the psoriasis area-and-severity index score (PASI 75) at week 12 (*primary endpoint*)¹
- 2) The proportion of subjects who have a reduction of 90% or more from baseline in the psoriasis area-and-severity index score (PASI 90) at week 12²
- 3) The proportion of subjects who achieve a score of 0 (clear) on a 5-point modified investigator's global assessment (IGA) at week 12³

1,2,3The 3 co-primary endpoints are subject to a step-down hierarchical closed testing procedure. (Primary objective is achieved if any null hypothesis is rejected following the order: PASI75, PASI90, IGA0).

12.8 * Secondary Outcome(s)

Indicate which *additional variable(s)* will be assessed to judge the secondary outcome(s). Give measurement units, if applicable.

- 1) The proportion of subjects who experience a psoriasis relapse at any time between week 24 and week 72. Psoriasis relapse is defined as loss of > 50% of the initial PASI improvement measured at week 24.
- 2) Severity of the relapses over the observation period.
- 3) Extent of relapse over the observation period.

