- 4) Elapsed time from week 24 until relapse occurs before week 72, measured in weeks.
- 5) The proportion of subjects who achieve a PASI 100 or PASI 90 response at week 12
- 6) Frequency and severity of all AEs and SAEs that occur during the whole trial including the observational period (AEs and SAEs include but not limited to comorbidities, such as hypertension, diabetes, and cardiovascular diseases).

12.9 * Methods and Procedures

Please provide a description of the laboratory and clinical analyses and procedures that will be performed. Include the role of external collaborators and consultants when appropriate. Please refer to Help text for Guidance.

The trial will be conducted as a unicenter, randomized, double-blind, parallel-group, placebo-controlled exploratory study of Secukinumab in subjects with mild plaque-type psoriasis. The purpose of the study is to evaluate the efficacy and the safety of Secukinumab for 3 or 6 month treatment periods, and to explore whether relapse occurs after the medication has been discontinued, during the subsequent 12 month observation period.

Arms: (Group 1: 6 months of Secukinumab) vs. (Group 2: 3 months of Secukinumab). Patients will be randomly assigned in a 1:1 ratio to Group 1 or Group 2. Group 1 receives Secukinumab at a dose of 300 mg with injections administered once weekly at baseline and at weeks 1, 2, 3, and 4 and then every 4 weeks for 6 months of period until week 12.

Patients randomly assigned to Group 2 will receive placebo injections corresponding to the Group 1 regimen until week 8 in order to maintain a double-dummy design until week 12. However, Group 2 will receive Secukinumab at a dose of 300 mg with injections administered **once weekly at week 12 and at weeks 13, 14, 15, and 16 and then every 4 weeks for 3 months** of period. Both group 1 and 2 discontinue Secukinumab after week 24 being observed from week 25 to week 72 (48 weeks).

Both Group 1 and Group 2 patients will not receive topicals or any other therapies except Secukinumab during the study periods, including placebo and observation periods.

Secukinumab is dosed weekly for the first 4 weeks (ramp up) the monthly (maintenance). In order to maintain the blind for the 2 dose groups, group 1 will resume weekly injection weeks 12 through 16. The injections given at weeks 13, 14, and 15 will be placebo.

Visit	Group 1		Group 2		Skin biopsy & blood
1	Screening	Screening			

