Langley et al. (2014) presented the results of two Phase 3 trials for Secukinumab: ERASURE and FIXTURE. Among others outcomes Langley reported the proportion of subjects with moderate or severe Psoriasis who achieve PASI75 (PASI score improvement over 75%) after 12 weeks of treatment in the 2 cohorts treated with Secukinumab 300 mg and the 2 Placebo cohorts with 245, 323, 246 and 324 subjects respectively. The worst scenario observed on Langley's results is: largest Placebo proportion=0.05 and smallest Secukinumab proportion=0.77. Assuming Langley's results as preliminary data, to find significant differences between groups by using a one-tail Fisher exact test with power equal to 0.95 and 99.9% of significance level, a sample size of 19 patients at each group (N=38) will be required. Considering the 5.6 % of dropout reported by Langley will be necessary to recruit 20 patients for each group (N=40). Power analysis for 3 co-primary endpoints and 19:19 patients is reported in the following table:

ENDPOINT	TREATMENT OBSERVED PROPORTION *	PLACEBO OBSERVED PROPORTION *	OBSERVED EFFECT SIZE*	SIGNIFICANCE LEVEL	POWER	DETECTABLE EFFECT SIZE
PASI 75	0.77	0.05	0.72	0.05	0.8	0.49
				0.05	0.9	0.55
				0.05	0.95	0.60
				0.01	0.8	0.42
				0.01	0.9	0.48
PASI 90	0.54	0.02	0.52	0.05	0.8	0.4
				0.05	0.9	0.47
				0.05	0.95	0.52
				0.01	0.8	0.52
				0.01	0.9	0.59
IGA0	0.24	0.01	0.23	0.05	0.8	0.37
				0.05	0.9	0.44
				0.05	0.95	0.50
				0.01	0.8	0.50
				0.01	0.9	0.56
				0.01	0.95	0.61

OR

ENDPOINT	TREATMENT OBSERVED PROPORTION *	PLACEBO OBSERVED PROPORTION *	OBSERVED EFFECT SIZE*	SIGNIFICANCE LEVEL	ESTIMATED POWER TO DETECT OBSERVED EFFECT SIZE
PASI 75	0.77	0.05	0.72	0.05	0.99
				0.01	0.99

PASI 90	0.54	0.02	0.52	0.05	0.99
				0.01	0.94
IGA 0	0.24	0.1	0.14	0.05	0.46
				0.01	0.25

* Langley et al. (2014)

2. Power Analysis for Exploratory Objectives/First outcome

Assuming the proportion of 300 mg secukinumab patients who achieve PASI 100 at week 24 as reported by Langley (0.4), the allocation ratio of subjects who achieve PASI 100 and subjects who not achieve PASI 100 for Group 1 (6 month of Secukinumab) will be 8:11. On that case a Fisher exact test to compare the proportion of patients who experience relapse with power equal to 0.80 and 95% of significance level will be able to detect significant differences only if the following relationship between proportions is observed:

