Proportion of patients from Group 1, who achieve PASI 100 at week 24 and experience relapse	Proportion of patients from Group 1, who not achieve PASI 100 at week 24 and experience relapse
0.00	0.45
0.13	0.73
0.25	0.82
0.38	0.91
0.50	1.00

Assuming the proportion of 300 mg secukinumab patients who achieve PASI 100 at week 12 as reported by Langley (0.3), the allocation ratio of subjects who achieve PASI 100 and subjects who not achieve PASI 100 for Group 1 (6 month of Secukinumab) will be 6:13. On that case a Fisher exact test to compare the proportion of patients who experience relapse with power equal to 0.80 and 95% of significance level will be able to detect significant differences only if the following relationship between proportions is observed:

Proportion of patients from Group 2, who achieve PASI 100 at week 24 and experience relapse	Proportion of patients from Group 2, who not achieve PASI 100 at week 24 and experience relapse
0.00	0.54
0.17	0.77
0.33	0.85
0.50	1.00

With the previous assumptions, the allocation ratio of subjects who achieve PASI 100 in Groups 1 and 2 will be 8:6. On that case a Fisher exact test to compare the proportion of patients who experience relapse with power equal to 0.80 and 95% of significance level will be able to detect significant differences only if the following relationship between proportions is observed:

Proportion of patients from Group 1 who achieve PASI 100 at week 24 and experience relapse	Proportion of patients from Group 2 who achieve PASI 100 at week 24 and experience relapse
0.00	0.67
0.13	0.83
0.25	1.00

3. Power Analysis for Exploratory Objective/Second outcome

To compare the time to relapse between groups with a sample size of 19:19 a Wilcoxon-Mann-Whitney test for nonrelated samples with power equal to 0.8 and 95% of significance level will be able to detect differences only if the effect size observed is equal or larger than 0.96

12.12 * Will samples be coded?

Yes No

If Yes, Please describe coding scheme consistent with GCP. If samples will not be coded, please provide justification for this proposed departure from GCP practice.

Samples will be coded using GCP with the following sequence

NSK__-001. NSK__-002, etc.

If available, upload the Data and Sample Sharing Management Plan approved by RU IT.

Version	Title	Category	Expiration Date	Document Outcome	Checked Out	View Document
No Document(s) have been attached to this form.						

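### Aim 4 compares relapse between arms only among patients who reach IGA 0, a post-randomisation subset expected to differ by arm, so a difference cannot be attributed to treatment duration

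*Combined protocol and SAP*

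**What the plan says.** - **Design (12.9).** "Patients will be randomly assigned in a 1:1 ratio to Group 1 or Group 2". Group 1 has 6 months of drug. Group 2 has 3 months of placebo, then 3 months of drug. Both stop at week 24 and are followed to week 72.
- **Aim 4 (12.6).** "To compare frequency of relapse between subjects who achieve a score of 0 (clear) on IGA between group 1 and group 2". No time point is given for IGA 0. The only one attached to an IGA 0 outcome is week 12, in 12.7.
- **Power (12.11).** This comparison is sized on PASI 100, not IGA 0: "the allocation ratio of subjects who achieve PASI 100 in Groups 1 and 2 will be 8:6". It sits under exploratory objectives, with "power equal to 0.80 and 95% of significance level".
- **Analysis (12.10).** Proportions are compared by Fisher's exact test. No covariate adjustment, principal-stratum analysis or caveat is described for the subset.
- **Other relapse analyses.** Section 12.8 lists relapse between weeks 24 and 72, and time to relapse, without restriction to cleared patients. Section 12.10 plans Wilcoxon-Mann-Whitney, Kaplan-Meier and log-rank analyses of relapse by group, and 12.11 sizes the time comparison at 19:19.

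**The concern.** Randomisation makes the two full groups comparable, but not the parts of them that clear. If 6 months of drug clears more patients than 3 months, Group 1's cleared subset contains patients who would not have cleared on the Group 2 course. Any difference in their underlying tendency to relapse then appears as an effect of duration, even if duration has none.

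Whether 3 or 6 months of drug prevents relapse after stopping is close to the study's stated purpose in 12.1. Aim 4 is the only aim that sets relapse frequency in one arm against the other, and it does so in this subset without a caveat.

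**Working it through.** **1. The plan's subset sizes.** Inputs from 12.11: 19 per arm ("a sample size of 19 patients at each group (N=38) will be required"), PASI 100 rates 0.4 (week 24) and 0.3 (week 12 of drug). The sentence with the 0.3 rate names Group 1, but the table below it is headed Group 2, and 8:6 requires Group 2.

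- Group 1: 19 × 0.4 = 7.6, so 8.
- Group 2: 19 × 0.3 = 5.7, so 6.

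The stated 8:6 reproduces, so the plan itself expects different selection by arm.

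**2. Bias if clearing is nested.** Assume that everyone who clears on 3 months would also clear on 6, and that duration has no effect on anyone's relapse. Of Group 1's cleared patients, 0.3/0.4 = 75% would clear on either course and 25% only on the longer one. Group 2's are all of the first kind.

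Spurious difference (Group 1 − Group 2) = 0.25 × (risk in 6-month-only clearers − risk in either-course clearers).

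| Assumed risk gap | Spurious difference |
|---|---|
| −0.2 | −0.05 |
| 0 | 0 |
| +0.2 | +0.05 |
| +0.4 | +0.10 |
| +0.6 | +0.15 |

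**3. The same, with a latent correlation.** Let ease of clearing and resistance to relapse be bivariate normal with a positive correlation, with the same relapse law in both arms and clearance cut at 0.4 and 0.3. Group 1 minus Group 2, in percentage points:

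| Overall relapse | Corr. 0.3 | Corr. 0.5 | Corr. 0.7 |
|---|---|---|---|
| 40% | 2.1 | 3.1 | 3.6 |
| 60% | 2.4 | 4.2 | 6.2 |
| 80% | 2.0 | 3.9 | 6.6 |

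The range is about 2 to 7 points. The positive sign follows from the assumed correlation.

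**4. Bias if clearing is not nested.** Let some patients clear only on the Group 2 course, with illustrative relapse risks for either-course, Group-1-only and Group-2-only clearers.

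- Either-course share 0.20, risks 0.4, 0.5, 0.9: Group 1 (0.20 × 0.4 + 0.20 × 0.5)/0.40 = 0.450; Group 2 (0.20 × 0.4 + 0.10 × 0.9)/0.30 = 0.567; difference −0.12.
- Either-course share 0.25, risks 0.4, 0.8, 0.8: Group 1 (0.25 × 0.4 + 0.15 × 0.8)/0.40 = 0.550; Group 2 (0.25 × 0.4 + 0.05 × 0.8)/0.30 = 0.467; difference +0.08.

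**5. Precision.** With relapse near 0.5 in both subsets, the standard error is √(0.25/8 + 0.25/6) = 0.27, or 27 points.

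**6. Time point.** At week 12 Group 2 has had only placebo. With the IGA 0 rates in 12.11, the subsets would be 19 × 0.24 = 4.6 patients against 19 × 0.01 = 0.2 or 19 × 0.10 = 1.9 (the two power tables give different placebo rates). That would compare drug clearers with placebo clearers, and steps 2 to 4 would not apply. Only a week-24 reading fits the question of duration.

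**7. Power of an all-randomised composite.** Define success as clear at week 24 and relapse-free to week 72, so its rate is clearance × (1 − relapse). The relapse rates are those of the plan's 8:6 table, read as 0/8 v 4/6, 1/8 v 5/6 and 2/8 v 6/6. Exact two-sided Fisher power at 0.05:

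| Relapse, Group 1 v 2 | Subset 8:6 | Composite success, Group 1 v 2 | Composite 19:19 |
|---|---|---|---|
| 0.00 v 0.67 | 0.68 | 0.40 v 0.10 | 0.46 |
| 0.13 v 0.83 | 0.70 | 0.35 v 0.05 | 0.56 |
| 0.25 v 1.00 | 0.89 | 0.30 v 0.00 | 0.72 |

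The composite loses 14 to 22 points. The plan labels all three rows as power 0.80, which none of the subset figures matches.

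**The case against.** The study calls itself exploratory, Aim 4's power is listed under exploratory objectives, and relapse and time to relapse are already planned without conditioning on clearance. With about 14 patients, sampling error swamps a bias of 2 to 7 points. The composite answers a different question: it can favour Group 1 only because more patients clear, and it has less power. All of this stands, and it limits the severity.

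It does not remove the point. The planned relapse outcome is measured against each patient's own week-24 PASI improvement, so it does not capture reaching and keeping clearance. No planned analysis combines the two across all randomised patients. Imprecision is a further reason not to read the subset as a treatment comparison.

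A reader might infer two stronger things.

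- *That the bias definitely runs against the longer course.* This needs nested clearing and lower relapse in easier clearers. The documents state neither. The power tables for Aim 3 do put lower relapse in cleared patients in every row, which makes that direction plausible but does not establish it.
- *That moving to the composite costs no power.* At the relapse rates in the plan's own table it does.

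**Conclusion.** Aim 4's between-arm comparison is not protected by randomisation, and the plan's own 0.4 v 0.3 shows that it expects the two subsets to be selected differently. A difference in either direction cannot be attributed to duration.

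The size and sign of the bias rest on inputs that the documents do not give. It is about 2 to 7 points against the longer course under the latent-correlation assumptions, −5 to +15 points for the nested risk gaps tried, and −12 to +8 points in the non-nested examples. The 0.4 and 0.3 are PASI 100 rates from moderate-to-severe disease, standing in for IGA 0 in mild disease. The change is worth making because it is cheap, but the bias is unlikely to dominate a comparison of 8 v 6 patients.

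**What to change.** 1. State that the conclusion on 6 versus 3 months rests on all randomised patients, using the relapse proportion and time-to-relapse comparisons already in 12.8 and 12.10.
2. Add the proportion with IGA 0 at week 24 and relapse-free to week 72, counting patients not clear at week 24 as failures, with the risk difference and 95% CI. Show clearance and relapse separately beside it.
3. Keep the IGA 0 subset comparison, read at week 24, as descriptive and labelled non-randomised. Reconcile IGA 0 in the aim with PASI 100 in the power section.

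The cost is one extra analysis and no extra visits, since PASI and a global assessment are scheduled from week 24 to week 72. The visit lists call that assessment PGA after screening, so the plan should confirm that it is the IGA scale. The downside is that the composite mixes clearing with staying clear and has less power than the subset at the plan's table rates (0.46, 0.56 and 0.72 against 0.68, 0.70 and 0.89). It should therefore be reported as an estimate with its interval and its two parts.

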2	baseline	baseline	Secukinumab 300 mg	Placebo	Skin biopsy & blood

3		week 1	Secukinumab 300 mg	Placebo	
4		week 2	Secukinumab 300 mg	Placebo	
5		week 3	Secukinumab 300 mg	Placebo	
6	month 1	week 4	Secukinumab 300 mg	Placebo	
7	month 2	week 8	Secukinumab 300 mg	Placebo	
8	month 3	week 12	check primary endpoint (IGA 0,1 at week 12)		Skin biopsy & blood
			Secukinumab 300 mg	Secukinumab 300 mg	
9		week 13	Placebo	Secukinumab 300 mg	
10		week 14	Placebo	Secukinumab 300 mg	
11		week 15	Placebo	Secukinumab 300 mg	
12	month 4	week 16	Secukinumab 300 mg	Secukinumab 300 mg	
13	month 5	week 20	Secukinumab 300 mg	Secukinumab 300 mg	
14	month 6	week 24	Secukinumab 300 mg	Secukinumab 300 mg	Skin biopsy & blood
15	month 9	week 36			
16	month 12	week 48	observation	observation	
17	month 15	week 60			
18	month 18	week 72	check secondary endpoint (recurrence)		Skin biopsy & blood
	*Optional skin biopsy and blood : when recurrence occurs after week 24				

Study Visits

Visit 1--Screening Visit/Enrollment

- Vital signs (weight, height, blood pressure, temperature, heart rate, respiration)
- Physical exam and questions your general health
- Serum pregnancy if female of child-bearing potential
- POCT HIV
- Blood for Hepatitis B (antibody as well antigen) and C, Comprehensive metabolic panel, Lipid panel, Hgb A1c, CBC and optional QuantFERON-TB Gold (only if no PPD screen)
- Assessment of psoriasis status using several scales: Investigator Global Assessment (IGA), Psoriasis Area and Severity Index (PASI) with BSA, Dermatology Life Quality Index (DLQI), PASE
- PPD / TB skin test or QuantIFERON-TB Gold

Visit 1.1--PPD Reading Visit

- If PPD was placed at Screening Visit, PPD reading 48 hours later
- Chest X-Ray. (If PPD Positive)

Visit 2--Baseline visit (and first dose)

- Medications history
- Physical exam (symptom driven as indicated)
- Vital signs (weight, body temperature, heart rate and blood pressure)
- POCT Pregnancy
- Fasting Blood PAX DNA/RNA, CBC, SST (serum storage) sample, Comprehensive Metabolic Panel, Lipid panel, and Hgb A1c.
- Two 6mm skin biopsies, 1 lesional, 1 non-lesional.
- Medical photography
- Assessment of psoriasis, PGA, PASI with BSA, PASE, DLQI
- Adverse event assessment
- Dose of Secukinumab or placebo by subcutaneous injection.
- Observation period of 15 minutes (+/- 5 minutes) post study drug administration
- Subject will be offered a meal at end of visit.

Visit 3 to 7 and 9 to 13 --(Week 1 to 8 and 13 to 20)

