- Assessment of psoriasis, PGA, PASI with BSA, PASE, DLQI
- Adverse event assessment

Translational research: 6-mm punch skin biopsies from lesional and non-lesional skin and blood samples will be obtained at baseline and weeks 12, 24, 72, at the time of psoriasis relapses, and at early termination. Genomic profiling of psoriasis skin will be conducted with the Affymetrix Human Genome U133 Plus 2.0 Array and RT-PCR. The phenotypes of activated T cells and regulatory T cells in psoriasis patients' blood will be studied by flow cytometry. Inflammatory and cardiovascular proteins in the blood will be investigated to develop a biomarker with Proximity Extension Assay technology (OLINK®).

Structure: Double Blind, Two-arm parallel group design, Randomized 1:1.

12.10 * Data Analysis

Describe method(s) of data analysis.

For the comparison between proportions a Fisher exact test will be performed in any case. The results will be presented as contingency tables and odd ratios will be calculated. 95% Confidence Intervals will be provided. To achieve the primary objective

The comparison between times of relapse must be done using a Wilcoxon-Mann-Whitney test. A Kaplan Meier analysis will be used to establish the relapse survival curve for each group and

the log-rank test will be made. A step-down hierarchical closed testing procedure will be done considering the order: PASI75, PASI90, IGA0.

12.11 * Explain the rationale for the choice of statistical measures and the number of participants proposed for the study, including the power calculations when applicable.

1. Sample Size Calculation for Primary Objective/First outcome (3 co-primary endpoints are subject to a step-down hierarchical closed testing procedure)

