13.11 Inclusion Criteria

Please list participant inclusion criteria:

Order Number	Criteria
1	Written informed consent must be obtained before any assessment is performed
2	18 years of age or older
3	Chronic plaque-type psoriasis for at least 6 months
4	Have a PASI between 6 and 12 and Body Surface Area (BSA) affected by plaque-type psoriasis less than 10% at screening
4	Negative PPD (negative chest w-ray if positive) or negative QuantiFERON-TB Gold.
5	Willing to wash off steroid creams and UVB therapy for 2 weeks prior to the baseline visit

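### For IGA 0, the unadjusted Fisher test at 19 per group gives one-sided power of 0.46; a pre-specified re-randomisation test using baseline PASI would give about 0.72-0.80, mostly by removing Fisher's discreteness

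*Combined protocol and SAP*

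**What the plan says.** Section 12.10 (Data Analysis) gives one rule for all proportions: "For the comparison between proportions a Fisher exact test will be performed in any case". It also promises contingency tables, odds ratios and 95% confidence intervals, and a step-down order of PASI 75, PASI 90, IGA 0. It does not say whether the tests are one- or two-sided. No stratified or covariate-adjusted analysis appears anywhere.

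Section 12.7 names IGA 0 at week 12 as the third co-primary. The primary objective is met if any null hypothesis is rejected in that order.

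Section 12.9 lists, at Visit 2 and before the first dose, "Assessment of psoriasis, PGA, PASI with BSA, PASE, DLQI". A pre-treatment PASI should therefore exist for every randomised patient. Section 13.11 limits its range at screening: "Have a PASI between 6 and 12 and Body Surface Area (BSA) affected by plaque-type psoriasis less than 10% at screening".

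Section 12.11 sizes the trial on PASI 75 "by using a one-tail Fisher exact test with power equal to 0.95 and 99.9% of significance level" and concludes that "a sample size of 19 patients at each group (N=38) will be required". Its two power tables disagree on IGA 0. The first has the row "IGA0 0.24 0.01 0.23 0.05 0.8 0.37" (placebo 0.01, difference 0.23). The second has "IGA 0 0.24 0.1 0.14 0.05 0.46" (placebo 0.1, difference 0.14, power 0.46).

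**The concern.** Aim 1 in section 12.6 concerns complete resolution of psoriasis, and IGA 0 is the only co-primary that measures clearance. It is also the only one with low stated power: on the plan's own figures, a true effect of the assumed size is missed more often than found.

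Part of that low power comes from the test and not from the sample size. With few responders in total, Fisher's p-value moves in large steps, and the test uses far less than its nominal 5%. A test that breaks those steps with a pre-treatment covariate already on file, and that gains a little more if the covariate predicts clearance, recovers much of the lost power without another patient. Section 17.1 says recruitment is closed, so the choice of analysis is one of the few ways left to improve this comparison.

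**Working it through.** **Inputs.** 19 analysed per group and one-sided testing (12.11). Allocation: "Structure: Double Blind, Two-arm parallel group design, Randomized 1:1" (12.9). IGA 0 rates of 0.24 and 0.01 (12.11, first table). Nominal level 0.05, with 0.01 as the plan's alternative. The documents give no association between baseline PASI and clearance, so it is assumed and varied.

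**1. The plan's own figure.** Exact power is the sum, over all pairs (x, y), of Bin(x; 19, p1) × Bin(y; 19, p0) for tables with one-sided Fisher p at or below alpha.

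| Rates | alpha | One-sided Fisher power | Printed |
|---|---|---|---|
| 0.24 v 0.01 | 0.05 | 0.456 | 0.46 |
| 0.24 v 0.01 | 0.01 | 0.254 | 0.25 |
| 0.24 v 0.1 | 0.05 | 0.173 | 0.46 |
| 0.24 v 0.1 | 0.01 | 0.060 | 0.25 |

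The printed powers therefore belong to a placebo rate of 0.01, not to the 0.1 printed beside them. Two-sided, Fisher gives 0.432 and 0.126 at 0.24 v 0.01.

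**2. Where Fisher loses power.** With four responders, all on secukinumab, p = C(19,4)/C(38,4) = 3,876/73,815 = 0.0525, just above 0.05. With five v none, p = 11,628/501,942 = 0.023. The 4 v 0 table has probability 0.2096 × 0.99^19 = 0.2096 × 0.826 = 0.173. Counting it as significant would move power from 0.456 to 0.456 + 0.173 = 0.629. Fisher's actual size at nominal 0.05 is 0.0009, 0.007 and 0.024 at common rates of 0.05, 0.10 and 0.24.

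**3. Unadjusted benchmarks (one-sided 0.05).** Boschloo's unconditional exact test: 0.630. Mid-p Fisher: 0.661. Fisher with a randomised decision at the boundary: 0.722.

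**4. Adjusted test.** Regress IGA 0 on Visit 2 PASI without a treatment term, sum the residuals in the secukinumab group, and refer that sum to its distribution under 1:1 re-randomisation. Simulation used 3,000 trials per scenario and 1,999 re-randomisations, with baseline PASI uniform over its range. The correlation is that of baseline PASI with response in the treated arm.

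| Assumed correlation | Power, one-sided 0.05 |
|---|---|
| 0 | 0.725 |
| 0.2 | 0.729 |
| 0.3 | 0.756 |
| 0.4 | 0.771 |
| 0.5 | 0.799 |

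A separate implementation, indexed by how well PASI discriminates responders, gave 0.72-0.73 with no discrimination and 0.79-0.81 at an area under the curve of 0.83. Two-sided, its range was about 0.57 to 0.70.

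**5. Size.** Simulated one-sided size of the adjusted test at nominal 0.05 was 0.042-0.051 at common rates of 0.05 and 0.24, 0.039-0.050 at 0.10, and 0.014-0.017 at 0.01.

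**6. Splitting the gain.** At correlation 0 the gain over Fisher is 0.725 − 0.456 = 0.269, all of it from removing discreteness. Baseline information adds 0.729 − 0.725 = 0.004 at correlation 0.2 and 0.799 − 0.725 = 0.074 at 0.5. The separate implementation puts the upper end near 9 points.

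**7. Other co-primaries.** PASI 75 already has power of about 0.99. PASI 90 moves from 0.94 to about 0.97-0.98 at one-sided 0.01, and is already near 0.99 at 0.05.

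**The case against.** The strongest objection is that most of the gain is tie-breaking. An uninformative covariate gives about the same power as flipping a weighted coin at Fisher's boundary (0.722). With pure-noise baseline values, the residual test declared 4 v 0 significant in 89% of draws, 5 v 1 in 54% and 3 v 0 in 47%, so identical response tables can pass or fail. Many statisticians dislike this, and preferring Fisher is defensible. The objection limits how the gain may be described. It does not make the test invalid, because re-randomisation controls its size, and unlike a coin flip it uses a relevant clinical measurement fixed before treatment.

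A reader might infer that power is 0.46 because baseline severity is ignored, and that adjusting for prognosis is what lifts it to 0.80. The documents do not support that. They give no PASI-clearance association, and the narrow entry range may make it weak.

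Three further points stand. One-sided testing is stated only for the sample size, so the two-sided comparison may be the relevant one. A residual p-value brings no odds ratio or interval and can disagree with the ones section 12.10 promises. And with recruitment closed, the documents do not show that week-12 results by group are still unseen.

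**Conclusion.** The point holds as a matter of test choice for IGA 0. Fisher is valid but very conservative here: power is 0.456 and true size is below 0.025 at common rates up to 0.24. The adjusted re-randomisation test reaches about 0.72-0.80 one-sided, or about 0.57-0.70 against 0.43 two-sided, with size at or below about 0.05. The lower end needs no assumption about prognosis. The upper end assumes a correlation near 0.5.

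All of this rests on a placebo rate of 0.01. At the 0.1 printed in the second table, Fisher power is 0.17 and the adjusted test reaches only about 0.29-0.35, so neither would be adequate.

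A reader might also infer that the trial's primary objective is underpowered. It is not: one rejection in order is enough, and PASI 75 comes first with power of about 0.99. What is at stake is whether the trial can make a confirmed statement about clearance.

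**What to change.** In section 12.10, for IGA 0:

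- Make the primary test a re-randomisation test on residuals from a regression of IGA 0 on Visit 2 PASI without a treatment term. This form still works when placebo has no responders (probability 0.826 at a rate of 0.01), whereas a logistic model with a treatment term would not give a finite estimate.
- Re-randomise according to the actual allocation scheme, which the documents describe only as 1:1.
- State the covariate, sidedness, number of re-randomisations and seed before unblinding. If week-12 results by group have already been seen, report the adjusted test only as a post hoc sensitivity analysis.
- Keep the step-down order. Keep Fisher, with the contingency table, odds ratio and 95% confidence interval, as the displayed summary and sensitivity analysis, and warn that the interval may not agree with the primary p-value.

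In section 12.11, reconcile the two IGA 0 rows, and restate power for the test actually chosen.

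The cost is a paragraph of wording and a short program, with no new data or patients. The downsides are a less familiar test, a decision that can turn on baseline values when response counts are the same, and a possible mismatch between p-value and interval. If the team will not accept the second of these, Boschloo's test (0.63 one-sided) is an unadjusted alternative with a smaller gain.
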